9.1.1 Primary end-points

1. Baseline characteristics of NVAF patients in the UK prescribed any of the three direct oral anticoagulants (DOACs) (rivaroxaban, dabigatran and apixaban) for the first time for stroke prevention
2. Daily dose, dose posology, naïve status, treatment duration of DOACs for stroke prevention in NVAF patients including those with renal impairment

9.1.2 Secondary end-point

1. Time-trends in the characteristics of first-time use of DOACs in NVAF patients

9.2 Setting

All patients aged ≥ 18 years with at least one year of enrollment with the PCP and one year since first health contact recorded in the database (THIN or CPRD) prior to index prescription date.

In the UK, nearly all residents are registered in a general medical practice that uses electronic medical records, grouped in databases that are available for research projects. The CPRD and THIN are two similarly structured, de-identified electronic medical record databases in the UK. To increase the number of patients available, both data sources would be pooled. Combining CPRD and THIN data will increase the size relative to the CPRD alone by approximately 25 to 30%. However, some practices provide data to both databases, therefore duplicate patients would be identified to avoid double-counting patients.

Among duplicate practices, it is anticipated that due to availability of free-text, the information from THIN will be retained. Therefore, we will use all THIN practices and only the information from CPRD practices that do not contribute to THIN. To identify and exclude duplicated practices between THIN and CPRD, and matching of anonymized patient characteristics will be applied (Cai et al., 2012, García-Rodríguez et al., 2014).

9.3 Variables

The following variables will be collected among the three study cohorts of DOACs:

- age and sex distribution at index date;
- dose of index drug at index date, dose posology, and duration of treatment (including pack size);
- type and duration of other anticoagulant use before the index date
- prior anticoagulation (DOACs, warfarin and LMWH) before index date: proportion of naïve patients (defined as those with no use of any anticoagulant ever prior to index date)
- use of specifically prescribed medications both in the year before the index date and year after the index date: antiplatelet drugs (low-dose acetylsalicylic acid, clopidogrel, dipyridamole, prasugrel, ticlopidine and ticagrelor); anticoagulants (including rivaroxaban, dabigatran, apixaban, warfarin, and LMWH), antiarrhythmic drugs, antihypertensive drugs, statins, anti-diabetic agents, non-steroidal anti-inflammatory drugs, oral steroids, acid-suppressive drugs, disease-modifying anti-rheumatic drugs, antidepressants, antipsychotic drugs, oral contraceptives, hormone-replacement therapy, strong inhibitors of either cytochrome P450 3A4 or P-glycoprotein (e.g. the systemic azole antimycotics ketoconazole, itraconazole, voriconazole and posaconazole and the HIV-protease inhibitor ritonavir), strong CYP3A4 inducers (e.g. rifampicin, phenytoin, carbamazepine or phenobarbital) and fluconazole.
- Renal disease (estimated glomerular filtration rate (eGFR) before index date as well as ACR (Albumin/Creatinine Ratio) where available.
- Comorbidity: haemorrhagic disease and history of intracranial haemorrhage, urogenital bleeding and gastrointestinal bleeding. Liver disease, pancreatic disease, cancer, cardiovascular disease (acute MI, coronary artery disease, congestive heart failure, ventricular arrhythmia, peripheral arterial disease) cardiovascular risk factors (hypertension, diabetes mellitus, hyperlipidaemia and obesity), stroke/TIA, respiratory disease (asthma and chronic obstructive pulmonary disease), rheumatoid arthritis, osteoarthritis, gastrointestinal disease, liver disease and pancreatic, alcohol-related disorders.
- CHADS₂ and CHA₂DS₂-Vasc scores will be calculated based on the presence/ history of congestive heart failure, hypertension, age, diabetes mellitus and prior stroke or transient ischaemic attack. HAS-BLED score for major bleeding risk (hypertension, renal disease, liver disease, stroke history, prior major bleeding or predisposition to bleeding, age > 65, medication usage predisposing to bleeding, alcohol usage history), will also be calculated .

- smoking status, body mass index (BMI) and Townsend score: most recently recorded value before the index date.
- healthcare utilization in the year prior to the index date and the year after (e.g. PCP visits, outpatient visits and hospital admissions).

Parameter	Description/ Definition
Demographic Characteristics at index date	
 • Age • Sex • Smoking status (previous 6 months) • Body mass index (previous 6 months) • Blood pressure history (previous 12 months) • Number of patients that are naïve vs non-naïve • For non-naïve: type and duration of anticoagulant used before index date
Risk factor categories	
 • CHADS₂ score • CHA₂DS₂ VASC • HASBLED score • INR measurement
Previous medical history (12 months prior to index date)	
 • Acute MI • Stroke or TIA • Systemic peripheral arterial embolism • Coronary artery disease • Congestive heart disease • Hypertension • Diabetes • Renal disease (eGFR) or ACR (Albumin/Creatinine Ratio)
Previous medication history (within previous 12 months of index date)	
 • Anti-arrhythmics • Statins • Anti-platelets • Beta-blockers • ACE inhibitors • Anti-diabetic agents • Non-steroidal anti-inflammatory drugs (NSAIDs) • Antacids • Histamine receptor antagonists • Proton pump inhibitors (PPIs) • Disease-modifying anti-rheumatic drugs (DMARDs) • Antidepressants • Antipsychotic agents • Oral contraceptives

	
• Hormone replacement therapy (HRT)• Strong inhibitors of Cytochrome P450 or P-GP• Strong inducers of CYP3A4
Previous use of VKA (ever prior to index date)	
• Warfarin• Other Vitamin K antagonist(s)
Concurrent (from index date) co-medication	
• Anti-coagulants• Aspirin• Clopidogrel• Other

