Vitamin K antagonists (VKAs) have been the standard treatment for antithrombotic prevention in atrial fibrillation (AF) in the last 60 years (NICE, 2016). Direct oral anticoagulants (DOACs) have shown to have a favourable balance between efficacy and safety compared with VKAs, and three (rivaroxaban, dabigatran, and apixaban) are now available and approved in the United Kingdom (UK) for the prevention of stroke in non-valvular AF (NVAF) patients.

Two classes of DOACs are currently available, the oral direct thrombin inhibitors (DTIs; e.g. dabigatran) and oral direct factor Xa inhibitors (e.g. rivaroxaban, apixaban, and edoxaban). Unlike VKAs, which block the formation of multiple active vitamin K-dependent coagulation factors (factors II, VII, IX, and X), these drugs block the activity of one single step in the coagulation cascade.

Individualized anticoagulant treatment should be based on patients' age, renal function, comorbidities, and concomitant treatments. The DOACs are new agents with several advantages including use of fixed-dosing with no need for INR monitoring, few interactions etc. The lack of effective antidote for some of them, their cost, or uncertainties in patients with kidney disease, and associated risk of bleeding may explain reservations in their widespread use (Hinojar et al. 2015).

There is a limited data on prescription and usage patterns of DOACs in routine care for stroke prevention in non-valvular atrial fibrillation (NVAF). Monitoring the usage patterns of DOACs is essential to study compliance with labelling information.

8. Research question and objectives

This population-based descriptive study will characterize first-time users of three DOACs in NVAF patients for stroke prevention including those renal impaired. Additionally, it will assess patterns of drug utilization in routine general practice in the UK, using the Clinical Practice Research Datalink (CPRD) and The Health Improvement Network (THIN).

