9.4 Data sources

THIN

Established in 2002, THIN now collects data from 570 practices, covering 6% of the general population, with more than 65 million patient-years of experience (CSD Medical Research, 2012). Eleven million individual patients are represented in the data; of those, approximately one-third are active at any one time. THIN records information on all services provided by the PCP, and information on specialist visits and hospitalizations are routinely forwarded to the PCP, who enters that information into the medical record. The population included in THIN is representative of the UK as a whole in terms of age, sex and geographic distribution (Bourke, Dattani et al. 2004; Blak, Thompson et al. 2011). THIN has been extensively validated for use in pharmacoepidemiology (Lewis, Schinnar et al. 2007).

The Read classification is used to code specific diagnoses as reasons for each consultation (O'Neil, Payne et al. 1995; Stuart-Buttle, Read et al. 1996), and a drug dictionary based on data from the MULTILEX classification is used to record prescriptions (First Data Bank 2014).

CPRD

The CPRD (<http://www.cprd.com/intro.asp>) contains diagnostic and prescribing information recorded by GPs as part of their routine clinical practice in the UK. The CPRD has information on 5.4 million individuals (active contributors), which represents approximately 9% of the UK population. These data are linkable, at least partially, with other health care data sets (e.g., hospitalization and national mortality data). Updated, valid, linked data are available through the CPRD Division of the UK Medicines and Health Care Products Regulatory Agency.

As in THIN, The CPRD also includes information recorded by GPs on patient demographics and lifestyle factors and detailed information on prescriptions written by the PCP. Free text comments are not available in CPRD.

The CPRD patients are representative of the UK population in terms of age and sex; it has been validated previously for use in pharmacoepidemiology to address a wide range of study questions in the European population (Herrett et al. 2015). Research at the CPRD requires approval from the CPRD Independent Scientific Advisory Committee (ISAC).

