9.7 Data analysis

The analysis will be based on descriptive statistics: frequencies and percentages will be calculated to the variables of interests, continuous and count variables will be described using mean (\pm standard deviation), proportions, median (quartiles) and minimum and maximum values. 95% confidence intervals will be computed for descriptive variables. The following outcomes will be assessed:

- Describe the three study cohorts i.e. patients prescribed with rivaroxaban, dabigatran, apixaban by baseline characteristics, use of medications, comorbidities and healthcare utilization services

(see all the variables in section 9.3) among the three study cohorts and contrast them with the baseline characteristics of patients in clinical trials.

- Use of study medications: Dose at first Rx, dose posology, duration of treatment (time on index medication), discontinuation, switch to another study drug .
- To assess the proportion of patients that are dosed in accordance and non-accordance to label, in study population and in subset of patients with renal impairment
- Contrasting patient characteristics of those prescribed DOACs with the corresponding characteristics in patients participating in clinical trials.

Table 1: Dosing of each study drug in the study population.

	Rivaroxaban	Apixaban	Dabigatran
Low dose Renal impairment Other indication to reduce the dose Non- accordance to label			
Standard dose incl.documented renal impairment			
All			

- Use of medication before index date will be categorized as:
 - Concurrent use (when the drug supply lasts until index date or is prescribed at index-date)
 - Recent (when the drug supply ends 1-30 days before index date)
 - Past use (when the drug supply ends 31-365 days before index date)
 - Non-use: no use in year before index date

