9.9 Limitations

- Given the nature of real-world data, missing data are likely to be present in a minority of instances.
- Only prescriptions captured in the CPRD and THIN dataset will be available. Medications prescribed at hospital will not be captured nor will over the counter medications (OTC).
- Incomplete data concerning medication compliance: drug use is based on prescriptions written by the treating physician, but no information is available to confirm if the drug was actually taken by the patient (common to virtually any computerized clinical database).
- There may be some missing data if GPs may not enter the hospitalization data however we expect that the vast majority of GPs will record information on hospitalization into THIN or CPRD (in practices not linked to HES).
- Some lifestyle variables such as smoking, BMI and alcohol consumption is not consistently recorded for all patients.
- The results from the three study cohorts should be interpreted with care, as in the presence of confounding, any findings cannot simply be attributed to the treatments defining the cohorts.

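### Duration of prior anticoagulant use is visible only back to the start of each patient's record, yet is summarised as if every value were complete

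*Protocol*

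**What the plan says.** - **The variable.** Section 9.3 lists "type and duration of other anticoagulant use before the index date". The parameter table in the same section repeats it under demographic characteristics at index: "For non-naïve: type and duration of anticoagulant used before index date". It therefore belongs to the first primary end-point in 9.1.1, baseline characteristics.
- **Look-back.** The parameter table gives 6 months for smoking and BMI, and 12 months for blood pressure, medical history and medication history. It gives none for this duration, and it seeks VKA use over the whole time before index.
- **Minimum record.** Section 9.2 admits adults "with at least one year of enrollment with the PCP and one year since first health contact recorded in the database" before index.
- **Source.** Section 9.9 states: "Only prescriptions captured in the CPRD and THIN dataset will be available". It names hospital and over-the-counter medication as uncaptured. It does not mention use that began before the record did.
- **Summary.** Under 9.7, "continuous and count variables will be described using mean" with standard deviation, median with quartiles, minimum and maximum. No provision is made for incomplete durations.

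**The concern.** One year is a floor, so look-back differs from patient to patient. Suppose one patient has taken warfarin for 10 years and joined the practice 13 months before index: the record can show 13 months at most. Another has taken it for 3 years and has 15 years of record: the record shows the correct 3 years. Section 9.7 averages the two as equals. The first value is censored: the patient is in the cohort, but the start of treatment lies before observation.

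Long earlier use is plausible in this population, since section 7 says that VKAs "have been the standard treatment for antithrombotic prevention in atrial fibrillation (AF) in the last 60 years". At stake is how long patients had been on an anticoagulant before starting the study drug. Through this mechanism the reported figure can only be too low.

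**Working it through.** The protocol gives no expected duration and no pre-index record length, so there is no figure of its own to reproduce. What follows shows the direction of the error exactly and its size under stated assumptions.

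**Direction.** Let T be the true time from the start of prior use to index and C the length of record before index. What can be observed is min(T, C). This equals T when use began inside the record and is less than T otherwise. With the minimum record, C is about 1 year and the value cannot exceed about 1 year.

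**Assumed model.** T is exponential with mean m. C is 1 year (the 9.2 minimum) plus an exponential amount, with total mean r. T and C are independent, and prior use runs up to index. Then:

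- share cut off at record start = P(T > C) = exp(−1/m) × m/(m + r − 1)
- mean of min(T, C) = m × (1 − share cut off), so the proportional shortfall in the mean equals the share cut off.

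**Inputs.** m = 2, 4 and 6 years and r = 5.9, 9 and 13 years are all assumptions. The lowest r borrows a figure from section 9.4, which describes THIN "with more than 65 million patient-years of experience" and eleven million patients: 65/11 = 5.9 years per patient. That is whole-record time for everyone ever in THIN, not the pre-index record of NVAF patients, so it serves only as a scale.

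**Shortfall in the plain mean:**

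| r (years) | m = 2 | m = 4 | m = 6 |
|---|---|---|---|
| 5.9 | 17.6% | 35.0% | 46.6% |
| 9 | 12.1% | 26.0% | 36.3% |
| 13 | 8.7% | 19.5% | 28.2% |

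Worked cell, m = 4 and r = 5.9: exp(−0.25) × 4/8.9 = 0.779 × 0.449 = 0.350, so the mean falls from 4 to 2.60 years. The true median is 4 × ln 2 = 2.8 years. The observed median solves t/4 + (t − 1)/4.9 = 0.693, giving 2.0 years. The share above 5 years falls from exp(−1.25) = 29% to exp(−1.25 − 4/4.9) = 13%.

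**Wider assumptions.** A simulation with m = 2, 5 and 8 and r = 3, 6 and 10 years (400,000 draws each) gave 11% to 71% of durations cut off. At m = 5 and r = 6, the mean fell from 5.01 to 2.96 years and the median from 3.47 to 2.23.

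**Candidate remedies.**

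1. *Kaplan-Meier in backward time, censored at record start.* This recovered the true median in all nine simulated settings. At m = 5 and r = 6 it gave 3.48 against a true 3.47; at m = 8 and r = 6, 5.55 against 5.54.
2. *Categories < 6, 6 to < 12 and >= 12 months.* Since C is at least 1 year, min(T, C) falls in the same category as T. For use that runs up to index, the table is unbiased whatever the record length.
3. *Mean or median only in patients with 12 anticoagulant-free months of record before the first prescription.* This keeps patients with T ≤ C − 1 and so removes long-term users. The mean becomes m(r − 1)/(m + r − 1), a shortfall of m/(m + r − 1). That exceeds the plain shortfall by the factor exp(1/m) in every setting: 14% to 55% against 9% to 47%. At m = 4 and r = 5.9, the mean is 4 × 4.9/8.9 = 2.20 against a plain 2.60, and 4.9/8.9 = 55% of users are kept.

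**The case against.** The strongest reply is that the protocol only names the variable. It nowhere says that duration is counted from the record start, and rules for start dates, gaps and supply commonly sit in a statistical analysis plan, which is not at hand. Section 9.7 also allows frequencies and percentages, so categories are already possible, and its concurrent, recent and past classes stay within 365 days of index. In part this stands: the cut-off is a consequence of using recorded prescriptions only, and it affects only patients already treated when their record began. It does not remove the point. The one-year floor, the reliance on captured prescriptions and the uncensored summaries are all fixed in the protocol, and the 365-day classes describe recency, not duration.

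A second reply concerns size, and it stands in full. The 5.9 years is not specific to NVAF patients starting a DOAC and says nothing about CPRD. True VKA duration, and its independence from record length, are assumed.

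Two stronger inferences are tempting and unsupported. A reader might take 35%, or any other cell, as the expected bias; the documents give no basis for choosing one. A reader might also conclude that contrasts between drugs, or the calendar trends in the secondary objective, are distorted. That could happen if record length differs by cohort or index year, but nothing in the protocol shows that it does.

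**Conclusion.** The point holds. Followed as written, sections 9.2, 9.3 and 9.7 produce a mean and median of prior anticoagulant duration that mix complete values with lower bounds, and no other section corrects or discloses this. The direction of bias is certain wherever some patients were already treated at record start. The 9% to 47% range rests on the exponential model and the assumed means, and is illustrative only. One descriptive variable, in non-naïve patients, is affected. No hypothesis or sample size depends on it. Severity is minor to moderate.

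**What to change.** - In 9.3, flag a prior-anticoagulant duration that reaches back to the record start as 'at least x', and count these patients per cohort.
- In 9.7, report duration for all non-naïve patients in categories that the one-year minimum supports, for example < 6, 6 to < 12 and >= 12 months. Where prior use stopped before index, keep the flag, because the visible stretch of that use can be shorter than a year.
- If a median is wanted, take Kaplan-Meier quantiles in backward time, censored at record start, and state the assumption that record length is independent of duration.
- Show the length of record before index per cohort, so that a reader can judge whether cohorts differ in look-back.
- Add the limitation to 9.9.
- Do not restrict the mean or median to patients with 12 anticoagulant-free months, since this increases the downward bias.

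The cost is a few sentences and one flag from dates already extracted. The only loss is that a plain mean is no longer the headline summary for this variable.

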9.6.1 Strategy for handling missing data

As a general strategy, no data imputation strategies will be applied to supplement missing data. The requirement for inclusion is complete data for critical variables; otherwise this individual is not eligible to be a member of the study population. However, missing values may occur in a small proportion. In this case, individuals with missing values will be kept in the analysis and a separate category will be created for missing values of that variable.

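### Duration of earlier anticoagulant use is planned as a plain mean and median, although for use already running when the record begins it is only a lower bound, so the summary is biased low

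*Protocol*

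**What the plan says.** Section 9.3 lists "type and duration of other anticoagulant use before the index date" among the variables for all three cohorts. The parameter table in the same section repeats it as a baseline item: "For non-naïve: type and duration of anticoagulant used before index date". The table's row on earlier VKA use looks back over all time before index, which in practice means as far as the record goes.

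Section 9.2 sets the minimum history at "at least one year of enrollment with the PCP and one year since first health contact recorded in the database". Above that minimum, look-back differs from patient to patient.

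Section 9.7 says that "continuous and count variables will be described using mean" with standard deviation, median with quartiles, minimum and maximum, and it refers back to all the variables of 9.3. Section 9.6.1 adds that "no data imputation strategies will be applied to supplement missing data". Nothing in these sections separates a spell that starts inside the record from one already running when the record opens. Section 9.9 does not name treatment begun before the record as a limitation.

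**The concern.** A patient who joins a contributing practice while already on warfarin has a recorded duration equal to the time since joining, not the time since starting. With the one year of history that the protocol permits, ten years of warfarin would be entered as about one year. The error goes in one direction only: a recorded spell can be shorter than the true one, never longer. The planned maximum would in part describe the longest record held.

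Prior-treatment duration helps to show who is being moved to a DOAC, and so forms part of the baseline description in the first primary objective (8.1). If it partly measures length of registration, contrasts of it between drugs or index years would be hard to read. The point concerns the duration value in patients correctly recognised as non-naïve. Prior users wrongly counted as naïve because their treatment ended before the record are a separate matter.

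**Working it through.** The protocol gives no figure for prior-use duration, so there is none to reproduce.

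**Inputs from the protocol.** The minimum look-back is 1 year (9.2). For THIN, section 9.4 gives more than 65 million patient-years and says "Eleven million individual patients are represented in the data". Hence 65/11 = 5.9 recorded years per patient. This averages all THIN patients and covers time before and after any index date, so it serves only as a plausible mid-value for look-back.

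**Assumptions, not in the documents.** True duration T is exponential with mean m. Look-back L = 1 + an exponential with mean k, so mean look-back is 1 + k. T and L are independent, and use runs up to index. The recorded duration is min(T, L).

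**Formulas.**
- Share cut off: P(T > L) = e^(−1/m) · m/(m + k)
- Mean of recorded durations: m · (1 − share cut off)
- Median of recorded durations: m·ln 2 if this is below 1 year, because every look-back is at least 1 year; otherwise (ln 2 + 1/k)/(1/m + 1/k)

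**Mean look-back 5.9 years (k = 4.9).** For m = 5, the share cut off is 0.819 × 5/9.9 = 41%. The recorded mean is 5 × 0.587 = 2.93 years, and the recorded median is (0.693 + 0.204)/(0.2 + 0.204) = 2.22 years. The other rows follow in the same way. The last two columns come from simulation with 1,000,000 draws per row.

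| True mean (y) | Cut off | Recorded mean | True median | Recorded median | Median, observed starts only | Kaplan-Meier median |
|---|---|---|---|---|---|---|
| 1 | 6% | 0.94 | 0.69 | 0.69 | 0.63 | 0.69 |
| 2 | 18% | 1.65 | 1.39 | 1.27 | 1.06 | 1.39 |
| 5 | 41% | 2.93 | 3.47 | 2.22 | 1.80 | 3.47 |
| 8 | 55% | 3.62 | 5.55 | 2.73 | 2.19 | 5.55 |

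**Range.** Under this model the relative shortfall of the mean equals the share cut off. With mean look-back varied from 3 to 10 years, it runs from 4% (m = 1, look-back 10) to 71% (m = 8, look-back 3). If every patient had exactly the permitted one year, a true mean of 5 years would be recorded as 5(1 − e^(−1/5)) = 0.91 years, with 82% cut off.

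**Observed starts only.** Keeping only patients with T ≤ L favours short spells. With m = 6 (true median 4.2) and mean look-back of 3, 6 or 9 years, the plain medians are 1.8, 2.4 and 2.8 years and the observed-start medians are 1.2, 2.0 and 2.4. Leaving out everyone whose first prescription falls in the first 6 months of the record gives 1.1, 1.9 and 2.4.

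**Where to censor.** If a 6-month window defines the flag, some flagged spells did start inside it. For m = 5 and look-back 5.9, censoring flagged spells at their recorded time gives a Kaplan-Meier median of 3.8 years. Censoring them at the end of the window, that is at L − 0.5, gives 3.5, which matches the truth.

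**The case against.** The protocol only lists the variable. It gives no algorithm for prior duration, and spell construction is often left to a statistical analysis plan, which may exist here and is not shown. Section 9.7 also mentions frequencies and proportions, so bands are not ruled out. Section 9.9 warns that "Only prescriptions captured in the CPRD and THIN dataset will be available", which in principle covers treatment before the record. Prior duration is named in no objective or end-point; it enters only through the baseline characteristics.

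Much of this stands, and it limits the weight of the point. It does not remove it. The one-year minimum, the open-ended look-back and the plain summary are all set in this protocol, and applied as written they produce the bias. The sentence in 9.9 goes on to hospital and over-the-counter medication and does not tell a reader that the reported durations are minimums.

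A reader might infer three stronger things that the documents do not support:
- **That the bias is known to be large.** The result depends on an assumed duration. At a true mean of 1 year the median is untouched, and at 2 years it is 1.27 against 1.39.
- **That differences between drugs or calendar years will be artefacts.** For a fixed record start, look-back would lengthen by about 5.3 years between January 2011 and May 2016. With m = 6, going from 5 to 10.3 years of look-back would raise the recorded mean from 6(1 − e^(−5/6)) = 3.4 to 6(1 − e^(−10.3/6)) = 4.9 years. Patients joining and leaving practices would reduce this, and the protocol does not say that look-back differs by drug or year.
- **That treatment duration on the index DOAC is affected.** It is not, because that duration is counted forward from index.

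**Conclusion.** The point holds as a minor improvement. The direction is certain for any spell already running when the record begins: the recorded value is a lower bound, and a plain mean of such values is too low. The size cannot be derived from the documents. Under exponential durations independent of look-back, the bias in the median is negligible when true prior use averages about 1 year. It is large when prior use averages 5 years or more relative to the look-back: at a mean look-back of 5.9 years, the recorded median is 2.22 against 3.47 years for a true mean of 5, and 2.73 against 5.55 for a true mean of 8. The 5.9 years is a THIN-wide average and may not describe DOAC initiators. Only one descriptive baseline variable is involved, and no end-point or test depends on it.

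**What to change.** In 9.3 and 9.7:

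1. Call the variable 'recorded duration'. Flag non-naïve patients whose first recorded anticoagulant prescription falls at the start of their record, for example within the first 6 months, and report their duration as 'at least' the recorded time.
2. Summarise by a Kaplan-Meier median counted back from the end of the earlier spell, with flagged spells censored at the end of the flag window. Alternatively, use duration bands with a separate 'start not observed' row. The Kaplan-Meier median assumes that true duration is unrelated to record length; the bands do not need this.
3. Do not give the median only in patients with an observed start, because that selects short durations and increases the downward bias.
4. Show the length of pre-index record by drug and index year, so that a reader can judge whether contrasts follow look-back.
5. Add one sentence to 9.9 on treatment begun before the record.

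The cost is one derived flag from dates already held, a sentence or two of text, and an extra row or two in the baseline table.

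### Section 9.3 gives CHA₂DS₂-VASc the inputs of CHADS₂, leaving out vascular disease and sex, so the score as written falls short of the full score by one point per missing item

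*Protocol*

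**What the plan says.** Section 9.3 of the protocol introduces CHADS₂ and CHA₂DS₂-VASc together and says that the "scores will be calculated based on the presence/ history of congestive heart failure, hypertension, age, diabetes mellitus and prior stroke or transient ischaemic attack". One list serves both scores. The next sentence gives the bleeding score a list of its own: "HAS-BLED score for major bleeding risk (hypertension, renal disease, liver disease, stroke history, prior major bleeding or predisposition to bleeding, age > 65", and so on. The parameter table in 9.3 then names each score on a separate line without defining any of them.

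The same section collects the data that the second stroke score would need. Sex is covered by "age and sex distribution at index date". The comorbidity list includes "cardiovascular disease (acute MI, coronary artery disease, congestive heart failure, ventricular arrhythmia, peripheral arterial disease".

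The scores belong to the baseline description, which is the first primary end-point in section 9.1.1: "Baseline characteristics of NVAF patients in the UK prescribed any of the three direct oral anticoagulants (DOACs". Section 9.7 contrasts the section 9.3 variables with the baseline characteristics of trial patients. Sections 8.2 and 9.1.2 add time trends in the characteristics of first-time use.

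**The concern.** Two differently named scores cannot have the same inputs and both be right. The five listed items are those of CHADS₂. What sets CHA₂DS₂-VASc apart is a finer grading of age, an item for vascular disease and an item for sex category, and the list names neither of the last two.

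What is at stake is comparability. A score computed from the five listed inputs but reported as CHA₂DS₂-VASc would be set beside trial populations as if it were the full score, and the difference would partly reflect the missing items. The shortfall also depends on the share of women and the share with vascular disease. If either share differs between the three drug cohorts, or shifts over calendar time, part of any contrast or trend in the score would be lost or distorted.

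**Working it through.** The protocol states no score value or distribution, so there is no figure of its own to reproduce. The check compares the score from the listed inputs with the full score.

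**Inputs.** The five listed items come from section 9.3. The weights are those of the standard scores and are not printed in the protocol: 1 each for heart failure, hypertension and diabetes; 2 for stroke/TIA; age 0/1 in CHADS₂ and 0/1/2 in CHA₂DS₂-VASc; 1 each for vascular disease and female sex in CHA₂DS₂-VASc only.

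**Maxima.**
- CHADS₂: 1 + 1 + 1 + 1 + 2 = 6
- CHA₂DS₂-VASc from the listed inputs, with age graded 0/1/2: 1 + 1 + 2 + 1 + 2 = 7
- CHA₂DS₂-VASc in full: 7 + 1 + 1 = 9

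**Shortfall per patient.** Full score minus score as written = (1 if female) + (1 if vascular disease). Enumerating all 2⁶ × 3 = 192 combinations of the seven components confirms that this holds at every level of the other items:

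| | No vascular disease | Vascular disease |
|---|---|---|
| Men | 0 | 1 |
| Women | 1 | 2 |

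**Shortfall in the cohort mean.** If p is the share of women and v the share with vascular disease, the mean is low by p + v, whether or not the two are related. The share of patients losing at least one point is 1 − (1 − p)(1 − v) if the two are independent. The protocol gives neither p nor v for DOAC initiators with NVAF, so both are assumed:
- p = 0.35, v = 0.10: mean low by 0.35 + 0.10 = 0.45; share affected 1 − 0.65 × 0.90 = 0.415
- p = 0.45, v = 0.20: mean low by 0.65; share affected 1 − 0.55 × 0.80 = 0.56
- p = 0.50, v = 0.35: mean low by 0.85; share affected 1 − 0.50 × 0.65 = 0.675

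The only sex-specific figures in the protocol are the all-age AF prevalences in section 9.5, 2.47% in men and 1.56% in women. With equal numbers of men and women they imply 1.56 / (1.56 + 2.47) = 38.7% women among people with AF. That lies inside the assumed range but does not describe the study cohorts.

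**Between cohorts.** The error in a comparison of two cohorts, or of two calendar years, is the difference in p plus the difference in v. It is zero if the mix is the same. The protocol contains nothing from which to estimate it.

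**The case against.** The best reply is that nobody would program it this way. The protocol names a standard score, its name signals the missing items, the data are collected, and the sentence does not say that the listed inputs are the only ones. Read literally, the two stroke scores would differ only in how age is graded, which leaves little reason to report both. Item weights and age bands are also normally left to the statistical analysis plan, which is not at hand.

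Much of this stands. An analyst applying the standard score would get the right answer, and the absence of weights and age bands is no fault here. But the protocol is not silent on inputs. It states a list, and the list is wrong for one of the two scores it covers. The neighbouring sentence itemises the bleeding score separately, so the section does set out to define its scores. As the text stands, the correct calculation departs from the protocol.

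It is also fair to say that the scores are one line in a long descriptive list. They do not determine eligibility, renal classification or the dosing-accordance table. CHADS₂, whose inputs are complete, is reported too.

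A reader might go further in three ways that the documents do not support:
- **Patients moved into a low-risk group.** The protocol defines no CHA₂DS₂-VASc cut-off or risk category, and losing one or two points from a high score does not make it low.
- **A bias between the three drugs.** This follows only if their sex or vascular mix differs, and the documents give no evidence on that.
- **The same fault in HAS-BLED.** Its list, which ends with "medication usage predisposing to bleeding, alcohol usage history", has no labile-INR item. Patients naïve to anticoagulants have no prior VKA treatment on which to score one, so leaving it out can be a deliberate choice. It is not part of this point.

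**Conclusion.** The point holds: the input list in section 9.3 is wrong for CHA₂DS₂-VASc. The per-patient shortfall of 0, 1 or 2 points and the maximum of 7 instead of 9 rest only on the definition of the named score and on the sentence being programmed as it reads. The cohort figures, a mean about 0.45–0.85 points low with roughly 42–68% of patients affected, are illustrations. They rest on assumed proportions and, for the share affected, on independence of sex and vascular disease.

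The severity is moderate to minor. The score falls within a primary descriptive end-point and is to be set against trial populations, but no eligibility rule, hypothesis test or dosing classification depends on it, and a careful analyst would probably score it correctly anyway.

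**What to change.** In section 9.3, split the sentence into two. Keep the present five inputs for CHADS₂. Give CHA₂DS₂-VASc its own list: the same five plus sex category and vascular disease. Say which of the collected variables make up the vascular item, such as prior MI and peripheral arterial disease, and assess it on the same presence-or-history basis as the other items.

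The cost is about one sentence. Sex, acute MI, coronary artery disease and peripheral arterial disease are already among the section 9.3 variables, so no new variable is needed. Weights and age bands can stay in the statistical analysis plan.
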